Severe pain (Numerical Rating Scale >7/10)	Itching
Chest pain unrelated to surgery	

Table 4. Emergency medical interventions

Did the telemedicine center contact PACU clinicians for any of the following interventions:	
Intubation	Unplanned transfusion
Assisted ventilation	Naloxone administration
Cardiopulmonary resuscitation	Return to OR
Cardioversion	Other (free text box)
If Yes, please check all that apply:	
 PACU nurse already aware of the situation	
 PACU nurse unaware of the situation	
 PACU nurse disagreed with the assessment	
 PACU nurse had already spoken to the supervising physician regarding the situation	

Other (please describe):

*Only the telemedicine center will document the detection of urgent situations.

Table 5. Patient discharge readiness

At what time did the patient sufficiently recover to be discharged (case attending anesthesiologist contacted for discharge)?	
PACU Nurses	Telemedicine Center for PACU
Time anesthesiologist is contacted for discharge evaluation	Time ready for discharge
Aldrete Score at discharge	Aldrete Score at discharge
	Unable to determine patient's readiness for discharge
Modified Aldrete Scale Component and Scoring Parameters	If Unable to fully assess, select reason(s) why (Checkbox)
Respiration	 More patient information needed  Equipment issues  Patient cooperation  Other (free text box)
2 – Able to take deep breath and cough	
1 – Dyspnea / Shallow Breathing	
0 – Apnea	
O₂ Saturation	
2 – Maintains > 92% on room air	
1 – Needs O ₂ inhalation to maintain O ₂ saturation > 90%	
0 – Saturation <90% even with supplemental O ₂	
Consciousness	
2 – Fully awake	
1 – Arousable on calling	
0 – Not responding	
Circulation	
2 – BP ± 20mmHg pre-op	
1 – BP ± 20-50mmHg pre-op	
0 – BP ± greater than 50mmHg pre-op	
Motor Activity	
2 – Able to move 4 extremities voluntarily or on command	
1 – Able to move 2 extremities voluntarily or on command	
0 – Able to move 0 extremities voluntarily or on command	

Interaction Phase (3 months)

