Physiological derangements – Success will be measured (in the observation phase) by the ability of the telemedicine center clinicians to identify physiological derangements as they are occurring in the PACU. The extent to which the telemedicine center clinicians can identify these physiological derangements will be measured by comparing PACU nurse and telemedicine center assessment surveys for each patient (Figure 3).

Symptom identification and management – Success will be measured (in the observation phase) by the ability of the telemedicine center clinicians to identify treatable symptoms as they arise in the PACU. The extent to which the telemedicine center clinicians can identify these treatable symptoms will be measured by comparing PACU nurse and telemedicine center assessment surveys for each patient (Figure 3).

Emergency situations – Success will be measured (in the observation phase) by the ability of the telemedicine center clinicians to identify situations requiring emergency medical intervention as they are occurring in the PACU. By construction, any time the telemedicine center feels that an emergency situation is present, preserving patient safety mandates contacting the bedside clinician.

During each such contact, the telemedicine center clinician will ask if the PACU nurse was already aware of the situation, disagreed with the assessment, and had already spoken to the supervising physician regarding it. The occurrence of emergency medical situations will be extracted from the electronic health record, and the agreement between telemedicine center and PACU nurse assessments will be quantitated.

PACU discharge – Success will be measured by the ability of the telemedicine center clinicians to identify when patients are ready for discharge (observation phase [without communication] and interaction phase [active communication with patient and PACU clinicians]) (Figure 3). The impact of the telemedicine center on this key function will be examined based on feedback from key stakeholder focus groups (interaction phase; see *Aim 2*). The difference between sign-out times in the observation and the interaction phases will be compared.

Data collection methods and measures during the interaction phase

Aim 1: Demonstrate the potential utility of a telemedicine center for the PACU, to assist with PACU functions

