The accuracy of physiologic, symptom, and status assessments is less straightforward to analyze. At the heart of the proposal is the belief that telemedicine assistance will detect some abnormalities not caught (or caught later) by the bedside team and detect that the patient has adequate status for PACU discharge before the bedside nurse. Using the bedside assessment as a gold standard is therefore limited. Similarly, although we believe that abnormalities detected by either bedside or telemedicine are unlikely to be false positives, we have no way of assuring that. We also cannot reliably determine the timing of the bedside nurse's detection of an abnormality, as they may document it much later if they believe it does not require an immediate intervention.

Each status assessment event can occur multiple times for each patient; however, we are unlikely to accurately capture the bedside nurse's impression of the number of times an event occurred. We will therefore binarize the presence of each assessment type and display confusion matrices (count tabulations) for each assessment type, which we will summarize with Jaccard indices. The "null hypothesis" that these measures do not agree at all is not meaningful or the subject of this study. As described above, neither is a directional superiority hypothesis possible to evaluate. Final Aldrete scores will be assessed with pearson correlation, and a t-test of the difference in scores presented. Differences in ready-for-discharge times will be summarized as mean and standard deviation, with the null hypothesis of zero mean tested by t-test with a robust standard error.

Agreement of emergency medical status is unlikely to have enough events to be statistically compared. We will present cross-tabulations of (emergency detected by telemedicine center:

yes/no) and (PACU nurse: disagree, investigate and agree, already aware, physician contacted). The absolute rate of telemedicine center false positives (team disagrees), true positives (team unaware), true positives (team aware), and false negatives (team aware > 15 minutes prior or t never detects) will be presented with 95% confidence intervals.

Data Collection

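### Emergency recognition (Aim 1c) is summarised by absolute rates with no stated denominator and overlapping categories, not as the share of emergencies recognised

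*Combined protocol and SAP*

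**What the plan says.** All references are to the combined protocol and SAP.

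- **Success measure** (Emergency situations, under Interaction Phase): "Success will be measured (in the observation phase) by the ability of the telemedicine center clinicians to identify situations requiring emergency medical intervention" as these arise. The same paragraph adds an independent source: "The occurrence of emergency medical situations will be extracted from the electronic health record". It also promises to quantify agreement between telemedicine and nurse, but names no statistic for emergencies.
- **Analysis** (Statistical Methods, Secondary Outcomes): the plan will present "The absolute rate of telemedicine center false positives (team disagrees), true positives (team unaware), true positives (team aware), and false negatives". The false negatives are defined in the parenthesis that follows: "team aware > 15 minutes prior or t never detects) will be presented with 95% confidence intervals". I read the stray letter as telemedicine. No denominator is given, and neither sensitivity nor positive predictive value is named.
- **Cross-tabulation** (same section): emergency detected by telemedicine "yes/no) and (PACU nurse: disagree, investigate and agree, already aware, physician contacted".
- **When the nurse is asked** (Emergency situations): "During each such contact, the telemedicine center clinician will ask if the PACU nurse was already aware of the situation". The lead question of Table 4 matches this: "Did the telemedicine center contact PACU clinicians for any of the following interventions". The nurse checkboxes follow only if the answer is yes.
- **Who documents** (footnote to Table 4): "Only the telemedicine center will document the detection of urgent situations". The Observation Phase section repeats this restriction, yet also says that the nurse's post-discharge form covers Tables 2 to 5.

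**The concern.** The stated success measure is conditional on an emergency: of those that occurred, how many did telemedicine recognise? The planned summary does not take that form. If the absolute rates are per monitored patient, which is the likely reading but not a stated one, every true-positive and false-negative rate is capped by the emergency rate. A false-negative rate of about 2% could then be read as good performance when it means that every emergency was missed.

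The cross-tabulation does not supply the missing denominator. Its four columns are nurse responses to a telemedicine contact, so the not-detected row has nothing to put in them. The general plan for binarised confusion matrices and Jaccard indices does not help either, because nurses do not independently document emergencies.

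Aim 1c is a named aim and the sponsor intends to extend the model to more bays, so its result should be readable on its own terms.

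**Working it through.** **Inputs**
- Patients in the observation phase, where success is judged: n = 250 (Study Size).
- Number of true emergencies, k: not given. Secondary Outcomes says only that events will probably be too few for statistical comparison. I assume k from 1 to 10 (0.4% to 4% of 250).
- Denominator of the absolute rates: not stated. I assume patients.

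The plan gives no event count, rate or power for this outcome, so there is no figure to reproduce.

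**Step 1. Size on each scale.** Compare a center that recognises none of k emergencies with one that recognises all.

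Exact (Clopper-Pearson) 95% limits for x out of n: lower = Beta quantile 0.025 with parameters (x, n − x + 1); upper = Beta quantile 0.975 with parameters (x + 1, n − x). For x = 0 the lower limit is 0 and the upper limit is 1 − 0.025^(1/n). For example, 1 − 0.025^(1/250) = 1.46% and 1 − 0.025^(1/5) = 52.18%.

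| k | False-negative rate, none recognised (k/250) | False-negative rate, all recognised (0/250) | Sensitivity, none (0/k) | Sensitivity, all (k/k) |
|---|---|---|---|---|
| 1 | 0.4% (0.01 to 2.21) | 0% (0 to 1.46) | 0% (0 to 97.50) | 100% (2.50 to 100) |
| 3 | 1.2% (0.25 to 3.47) | 0% (0 to 1.46) | 0% (0 to 70.76) | 100% (29.24 to 100) |
| 5 | 2.0% (0.65 to 4.61) | 0% (0 to 1.46) | 0% (0 to 52.18) | 100% (47.82 to 100) |
| 6 | 2.4% (0.89 to 5.15) | 0% (0 to 1.46) | 0% (0 to 45.93) | 100% (54.07 to 100) |
| 8 | 3.2% (1.39 to 6.21) | 0% (0 to 1.46) | 0% (0 to 36.94) | 100% (63.06 to 100) |
| 10 | 4.0% (1.93 to 7.23) | 0% (0 to 1.46) | 0% (0 to 30.85) | 100% (69.15 to 100) |

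The true-positive rates are the mirror image: 0/250 for none recognised, k/250 for all. The two extremes differ by 0.4 to 4.0 percentage points on the absolute scale and by 100 points as sensitivity. The absolute-scale intervals still overlap at k = 8 (1.39 against 1.46) and are apart at k = 10 (1.93 against 1.46). The sensitivity intervals overlap at k = 5 (52.18 against 47.82) and are apart from k = 6 (45.93 against 54.07).

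**Step 2. Can sensitivity be rebuilt as TP/(TP + FN)?** Not safely, for three reasons.
1. If the team knew more than 15 minutes before telemedicine called, the nurse answers that she was aware, which makes the event a true positive (team aware). The same event meets the definition of a false negative. With k emergencies all eventually called, L of them late, TP = k and FN = L, so TP + FN = k + L, which exceeds k. For k = 5 and L = 1 (illustrative), six entries describe five emergencies. The ratio is 5/6 = 83%, against 4/5 = 80% if late counts as missed and 5/5 = 100% if it counts as detected.
2. True positives rest on nurse answers during a contact, while never-detected emergencies can come only from the health record. The reference standards differ, and the counting unit may too.
3. The 15-minute rule needs the time at which the bedside team became aware. Secondary Outcomes says, of abnormalities in general, that this cannot be reliably determined.

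**Step 3. The not-detected row.** Its columns are disagree, agree after investigating, already aware, and physician contacted. All are answers to a contact that, in this row, did not take place. The statement that the nurse form covers Tables 2 to 5 does not fill the row, because Table 4 itself asks only about contacts made by telemedicine.

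**The case against.** The strongest reply is that the plan does report misses. False negatives expressly include emergencies that telemedicine never detected, and the health record supplies them. A center that recognised nothing would show no true positives and k false negatives; a perfect one would show the reverse. A reader might infer from the near-zero rates that the first would look almost as good as the second. The documents do not support that: the two results are opposite, and the true-positive line alone shows it.

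A reader might also infer that the planned intervals cannot tell good recognition from none. That is not supported either. At 10 emergencies per 250 the absolute-scale intervals separate, and at 5 or fewer the sensitivity intervals overlap too. The study does not compare two such centers in any case. The plan also says openly that events will be few, and both the per-patient denominator and the event rate used here are assumptions. All of this stands, and it limits the point to scale and specification.

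One further objection shapes the remedy. Using health-record emergencies as the only reference would leave out an emergency that telemedicine found, the nurse had not noticed and then agreed with, but that was never recorded as one. The plan itself says that the bedside assessment is a limited gold standard. That stands, so the reference set needs to be wider than the health record.

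The reply does not remove the unstated denominators, the double classification of late detections, or the row without a data source.

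**Conclusion.** The point holds as a fault of scale and specification in a secondary outcome that carries a named aim. The planned rates do not express the stated success measure, their denominator is missing, and the overlapping categories stop a reader from safely deriving the success measure from them.

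For an assumed 5 emergencies among 250 patients and a per-patient denominator, recognising none and recognising all differ by 2 percentage points as planned, against 100 points as sensitivity. Across 1 to 10 assumed emergencies the planned difference is 0.4 to 4.0 points. The double classification and the row without nurse answers rest on the plan's own definitions and need no assumed figure. Misses are not concealed, and no reporting choice will make so few events precise.

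**What to change.** In Secondary Outcomes:

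1. Report sensitivity: emergencies recognised by telemedicine divided by all confirmed emergencies, where confirmed means extracted from the health record or called by telemedicine with the nurse's agreement. Because agreed calls count as recognised by construction, also report separately the share of health-record emergencies that were recognised.
2. Report positive predictive value: agreed calls divided by all telemedicine emergency calls.
3. Give counts, denominators, the counting unit (event or patient) and exact (Clopper-Pearson) 95% intervals for each.
4. Put each late detection in one category only. Count it as missed in the main analysis and as detected in a supporting one, since bedside timing is acknowledged to be unreliable.
5. Tabulate telemedicine yes/no against health-record emergency yes/no, and show nurse answers only within the yes row. Reconcile the statement that the nurse form covers Tables 2 to 5 with the Table 4 footnote.

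Keep the absolute rates as description.

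The cost is rewording plus two decisions, on the reference set and on late detections; the data are already planned. The intervals will be wide, for example 0/5: 0 to 52% and 5/5: 48 to 100%.

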In the first three months (the Observation phase) of this proof-of-concept study, a telemedicine center for the PACU will monitor patients assigned to two PACU bays. Both the telemedicine center and nurses caring for patients in the PACU bays will separately document physiological derangements (Table 2), treatable symptoms (Table 3), or a situation requiring urgent medical intervention (telemedicine center only; Table 4) during the PACU stay. Clinicians in the telemedicine center will assess when the patient meets discharge criteria, based on the modified Aldrete scale¹⁵ and their clinical judgment. They will document the time that discharge criteria are met, the modified Aldrete scale score at this time, and any additional relevant information. If clinicians in the telemedicine center judge that they are unable to determine a patient's readiness for discharge, they will document their reasons (Table 5). Clinical judgment will be used in determining appropriate discharge parameters for patients with pre-existing conditions. The telemedicine center clinicians will document each patient's information outlined in Tables 2-5 directly into REDCapTM (a secure web application for managing online surveys and databases) and AlertWatch. After a patient has been discharged from the PACU, the PACU nurse will fill out a form providing information outlined in Tables 2-5. This includes

information on physiological derangements, treatable symptoms, and discharge information. This form will be collected by the research team, and the information in the form will be documented in REDCap. During this phase of the study, clinicians in the telemedicine center will not communicate with clinicians in the PACU (nurses or physicians), unless there is a patient safety event.

Table 2. Physiological derangements and complications

Did the patient have any of the following physiological derangements:	Definition: (for study purposes)
Persistent confusion / delirium	
Tachycardia	HR >120/min
Bradycardia	HR <45/min
New onset atrial fibrillation	
Respiratory depression	<8 respirations per minute
Hypoxemia	<90% O ₂ Saturation
Hypotension	MAP <55
Weakness	<5/5 power in limbs
Emesis / vomiting	
Hyperglycemia	Glucose >200mg/dL
Hypothermia	Temperature < 35.5 C
Low urine output (for PACU stay >4h)	<0.5 ml/kg per hour

Table 3. Symptoms requiring treatment

Did the patient complain of the following symptoms:	
Dizziness or lightheadedness	Difficulty breathing
Nausea	Shivering

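### The 15-minute branch of the emergency false-negative rule needs a bedside awareness time that the listed items do not collect, so late-detected misses cannot be told apart from true positives in which the team was aware

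*Combined protocol and SAP*

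**What the plan says.** Statistical Methods, Secondary Outcomes, sets out four categories for emergencies, each to be reported as an absolute rate with a 95% confidence interval. The list opens with "The absolute rate of telemedicine center false positives (team disagrees), true positives (team unaware"), continues with true positives in which the team was aware, and ends with "false negatives (team aware > 15 minutes prior or t never detects"). I read the garbled second branch as the telemedicine center never detecting the event. The section also plans a cross-tabulation of telemedicine detection (yes/no) against the nurse's response.

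The data come from two places:

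- **Table 4**, completed when the telemedicine center contacts the bedside. Its checkboxes include "PACU nurse already aware of the situation", the corresponding unaware box and "PACU nurse disagreed with the assessment". Its footnote says "Only the telemedicine center will document the detection of urgent situations". The emergency paragraph under Interaction Phase lists the questions asked at each contact: whether the nurse was aware, disagreed, or had already spoken to the physician. None asks when.
- **The EHR.** The same paragraph says "The occurrence of emergency medical situations will be extracted from the electronic health record".

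On timing, Secondary Outcomes says of abnormalities in general: "We also cannot reliably determine the timing of the bedside" nurse's detection.

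**The concern.** A rule that turns on a 15-minute interval needs two times. The described items supply no time for the bedside end, and Table 4 lists no field for the telemedicine end either. Two of the four promised categories draw on the same yes/no box, and nothing recorded says which contact belongs in which.

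These are the only quantified error rates for Aim 1c. A confidence interval around a count that the data do not fix conveys precision that is not there, and the split would have to be chosen at analysis, possibly after the results are known. Secondary Outcomes expects too few emergencies for statistical comparison, so each ambiguous contact carries weight.

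A smaller gap goes with it. Because Table 4 starts from a telemedicine contact, an emergency that telemedicine did not detect generates no nurse response, although the cross-tabulation has a row for it.

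**Working it through.** The documents give no emergency rate, count or precision, so there is no figure of the plan's to reproduce. The check is to trace each category to a collected item.

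| Category | What the rule needs | Source described | Computable? |
|---|---|---|---|
| False positive | Team disagrees | Table 4 checkbox | Yes |
| True positive, team unaware | Team unaware | Table 4 checkbox | Yes |
| False negative, never detected | Emergency with no telemedicine detection | EHR extraction, for events the EHR records | Yes, once linked to the rule |
| False negative, aware more than 15 minutes before | Awareness time and telemedicine time | Yes/no box only | No |
| True positive, team aware | Aware, but not by more than 15 minutes | The same yes/no box | Not separable from the row above |

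**Size of the ambiguity.** Let M be never-detected emergencies, A already-aware contacts, U unaware contacts, and L the unknown number of A in which the gap exceeded 15 minutes (0 ≤ L ≤ A). Then:

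- false negatives = M + L, anywhere from M to M + A;
- true positives (team aware) = A − L, anywhere from A to 0;
- emergencies = M + A + U.

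The denominator is 250 patients, the planned size of the observation phase, where the emergency measure is assessed. The event counts below are assumptions. Intervals are exact (Clopper-Pearson).

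*M = 2, A = 6, U = 2 (10 emergencies):*
- lowest: 2/250 = 0.8% (95% CI 0.1% to 2.9%), or 2/10 = 20% of emergencies;
- highest: (2 + 6)/250 = 8/250 = 3.2% (1.4% to 6.2%), or 8/10 = 80% of emergencies;
- true positives (team aware) move the opposite way, from 6/250 = 2.4% to 0.

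*M = 1, A = 3, U = 1 (5 emergencies):*
- lowest: 1/250 = 0.4% (0.01% to 2.2%), or 1/5 = 20%;
- highest: (1 + 3)/250 = 4/250 = 1.6% (0.4% to 4.0%), or 4/5 = 80%.

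The per-emergency range is the same in both cases because its width is A/(M + A + U): 6/10 and 3/5, both 60 percentage points. A smaller already-aware share would narrow it in proportion.

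**Contrast.** With 2 assumed disagreements, the false-positive rate is 2/250 = 0.8% (0.1% to 2.9%) whatever the awareness times were.

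**The case against.** The strongest reply is that this is a descriptive secondary result in a proof-of-concept study, that the plan expects few events, and that no decision threshold hangs on these rates. The natural reading of the two categories is a clean split at 15 minutes, so the plan does not prescribe counting an event twice. The survey forms are left as a placeholder under Supplementary material, so the real form may hold a time field. All of this is fair and limits the weight of the point. It does not supply the missing time: the documents list none and define no proxy.

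A reader might infer more than the documents support:

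- *That none of the rates can be computed, including false positives.* Disagreement is the definition and has its own checkbox. The lack of an independent reference limits what the rate means, not whether it can be calculated.
- *That misses tend to zero by construction, or that telemedicine is made to look better.* The planned EHR extraction can supply never-detected events. The 15-minute rule moves aware contacts from hits to misses, which is strict on telemedicine. Without times they could be classified either way, so no direction of bias is shown.
- *That the plan says emergency timing cannot be determined.* The caveat covers abnormalities in general, and its reason is late charting of findings thought not to need immediate action. That reason does not carry over readily to Table 4 events. Even so, the plan names no EHR time to use in place of awareness.
- *That the plan contradicts itself on who records emergencies,* because "the PACU nurse will fill out a form providing information outlined in Tables 2-5". The Observation Phase text itself restricts Table 4 to the telemedicine center, and its description of the nurse form names derangements, symptoms and discharge only. This is loose wording to tidy.

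**Conclusion.** Wrong as written, for a secondary, descriptive outcome. The false-negative rate and the true-positive (team aware) rate, with their intervals, are not determined by the items the plan describes; the false-positive and team-unaware rates are. The false-negative count is uncertain by the full number of already-aware contacts: 2 to 8 of 10 emergencies under the assumed counts, or 0.8% to 3.2% of 250 patients. That size rests on assumed counts; the inability to separate the two categories does not. The not-detected row of the cross-tabulation has no nurse response and can be filled only from the EHR. The conclusion assumes that Table 4 and the contact questions are the complete record of each contact.

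**What to change.** 1. Add two times to the telemedicine contact record: when the telemedicine center detected the emergency, and when the bedside team says it became aware. Alternatively, name an EHR timestamp as the proxy for awareness. An intervention or charting time normally falls after awareness, so such a proxy would tend to understate the gap; the plan should say so.
2. Classify an already-aware contact as a false negative if the gap exceeds 15 minutes and as a true positive (team aware) otherwise. Table 4 allows several boxes to be ticked, so add a rule for a contact marked both aware and disagreed. The categories are then mutually exclusive.
3. Take never-detected events from an EHR list of the Table 4 interventions, use it for the not-detected row, and state the denominator of each rate. Counting every EHR event without an earlier telemedicine call as a miss would be simpler, but it would discard the plan's own 15-minute allowance and leave the awareness time without a use.
4. Report disagreement under that name.
5. Tidy the table range given for the nurse form.

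The cost is two fields on the contact record and a few sentences in the statistical section; the EHR extraction is already planned. The downside is that recalled awareness times are approximate. If the times are judged too poor to use, the 15-minute branch would have to be dropped and the false-negative rate limited to never-detected events.
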